
PI Name: [name]., Ph.D., M.Sc.

Abbreviated Title: GOAT

Version Date: 09/25/2023

will be analyzed, including calorie content of food and drink chosen, patterns of engagement with the food, order of food selection, time spent in the buffet, portion sizes selected, distribution of different food types on the plate, total calorie count of selected food with and without beverages, proportion of high calorie foods, sweetened beverage selection, spatial measurements, and food choice process. At the end of the procedure, participants will also fill out questionnaires to assess participant's experiences in the virtual environment.

5.4.3 Additional data that will be collected:

During the study, the following data will also be collected:

- Alcohol drinking patterns using the Alcohol Timeline Follow Back.
- Smoking patterns using the Smoking Timeline Follow Back.
- The E-cigarette Fagerström Test of Nicotine Dependence (e-FTND) [Only for tobacco vapers/e-cigarette users]
- The urge to drink alcohol will be assessed by the Alcohol Urge Questionnaire (AUQ).
- Food craving using the General Food-Cravings Questionnaire (GFCQ) Trait (at baseline of Stage 1) and State.
- Affective mood states using the Profile of Mood States (POMS-2).
- Measures of sleepiness and possible sedation will be monitored by Stanford Sleepiness Scale (SSS).
- Signs and symptom of alcohol withdrawal will be monitored by Clinical Institute Withdrawal Assessment for Alcohol-revised (CIWA-Ar).
- History of familial alcohol use problems will be assessed by The Family Tree Questionnaire (FTQ).
- Craving for alcohol will also be assessed by Penn Alcohol Craving Score (PACs).
- Anhedonia will be measured by The Snaith-Hamilton Pleasure Scale (SHAPS).
- Personal Preference Log to gather information on food and alcohol preferences for CR procedures.
- Dietary Conditions Log will be used to establish a menu for standardized meals during the study and to assess dietary restrictions and preferences that may affect the food choices in the virtual reality environment. Measurements of pain using the Symptom Checklist

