- Blood samples for will be drawn for pharmacokinetic (PK), pharmacodynamic (PD), and research use will be taken during STAGE 1 and STAGE 2 on each dosing day and the last Study Day. Additional blood samples will be taken on experimental days (Virtual Reality Study Procedure Day and Cue Reactivity Study Procedure Day). For all blood collection time points there are 2 x 3mL and 1 x 4mL samples collected for research bloods and 2 x 3mL samples collected for pharmacokinetics and pharmacodynamics. On Dosing Day 1, a 3mL blood sample will be taken for genetics. The genetic sample is meant to be collected for potential future exploratory analysis aimed at investigating pharmacogenetic aspects of GLWL-01. This is approximately 131mL per stage and the maximum PK/PD/research blood collected for the entire study period will not exceed 455mL for any given participant. (see "Use of Samples")

PI Name: [name]., Ph.D., M.Sc.

Abbreviated Title: GOAT

Version Date: 09/25/2023

section G below for details).

- Waist circumference will be assessed twice during each Stage (first and last day of each Stage) to calculate the body shape index (BSI), which is, compared to BMI, a better indicator of health risks related to weight fluctuations.

Suicidality Assessment will be performed using the Columbia Suicide Severity Rating Scale (C-SSRS) at baseline (day of consent) as well as the (Stage 2), last study day **or** day of discharge if the participant completes study participation prior to (Stage 2), last study day, whichever occurs first.

Upon determination that screening reveals signs of suicidal ideation or concerning behavior, a mental health evaluation will be performed. This evaluation will determine the level of risk and take appropriate steps to ensure the patient's safety.

Subject characterizations:

The following are characterization measures of various behaviors and preferences administered either in questionnaire or task form. With the exception of smoking all of these will be done once at the beginning of the study before study drug is administered. (please see— Study Outline for timing of these procedures).

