7 STATISTICAL ANALYSIS

7.1 *Analysis of data/study outcomes*

Outcome data will be examined for homogeneity of variance, and if necessary transformed to meet this criterion. As this is a within-subjects design, repeated measures analysis of covariance (ANCOVA) will be used to analyze the primary outcome, with drug condition as the within-subjects factor. Similarly, for secondary outcome measures such as food choices, repeated measured ANCOVA will also be used.

Biomarkers and hormonal measurements, such as feeding-related peptides stress-related hormones and/or inflammatory markers (see Section G,1), will also be correlated with changes in primary and secondary outcomes to explore the relationship between hormonal responses of interest and behavioral changes. A probability level of 0.05 or lower will be considered significant.

Potential covariates will be evaluated such that covariates that significantly predict the outcome measure will be retained in the model. Negative affect, as measured by the POMS-2 and Symptom Checklist, and cannabis dependence, if present, will be entered as covariates of particular interest in analysis for primary and secondary outcome responses. Additional covariates include baseline characteristics, like age, race, years of education, alcohol drinking levels, ADS score, family history of alcoholism density and number of days of alcohol abstinence prior to enrollment.

7.2 *Power analysis*

We performed a power analysis for the primary outcome and it is consistent with: 1) our previous Phase 1b study (N = 12 completers) with PF-5190457, where the primary outcome was the number of AEs experienced differ in the drug condition, compared to placebo; and 2) effect sizes ($dz = 0.5$) of alcohol cue-reactivity studies for other medications like the FDA-approved naltrexone and other experimental compounds (George et al., 2008; Miranda et al., 2014; Monti et al., 1999, 2000). The goal will be to reach up to 34 completers. A sample size of 43 subjects will be needed: a) considering the following parameters: $dz = 0.5$, α err prob = .05, and power ($1 - \beta$ err prob) = .80 (see Table 1 for additional details); and b) considering an attrition rate of approximately 20%.

PI Name: [name]., Ph.D., M.Sc.

Abbreviated Title: GOAT

Version Date: 09/25/2023

Table 1: Power Analysis

t tests - Means: Difference between two dependent means (matched pairs)

[figure not shown]
Analysis: A priori: Compute required sample size

Input:

Tail(s)	= Two

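### Does leaving the timing of the POMS-2 and Symptom Checklist covariates open in section 7.1 put the GLWL-01 effect at risk?

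*Combined protocol and SAP*

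**What the plan says.** Section 7.1 names the model: "repeated measures analysis of covariance (ANCOVA) will be used to analyze the primary outcome, with drug condition as the within-subjects factor". Covariates that significantly predict the outcome are kept. It then singles out two: "Negative affect, as measured by the POMS-2 and Symptom Checklist, and cannabis dependence, if present, will be entered as covariates of particular interest", for both primary and secondary outcomes. The next sentence reads "Additional covariates include baseline characteristics, like age, race, years of education", and continues with drinking history and similar items. No measurement time is attached to the two scales.

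Section 5.4.3 lists both scales under the lead-in "During the study, the following data will also be collected". The Symptom Checklist entry there is "Measurements of pain using the Symptom Checklist". One other instrument in that list, the trait food-craving questionnaire, is marked as a Stage 1 baseline measure; these two are not.

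Under Subject characterizations the protocol says "With the exception of smoking all of these will be done once at the beginning of the study before study drug is administered", but neither scale is on that list. The reader is sent to the "Study Outline for timing of these procedures". Sections 6.1 and 12 also cite that outline, for laboratory tests and ECGs. It is not in the text as supplied.

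**The concern.** Adjusting for a variable that treatment itself changes removes, or distorts, the part of the effect that runs through that variable. Both co-primary questions (does GLWL-01 lower cue-elicited craving, and does the AE count differ) concern total effects.

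Three features make the risk look real. Both scales sit among data gathered during the study, so on-treatment scores probably exist. The word baseline appears only in the following sentence, about a separate list of covariates. And the retention rule favours covariates related to the outcome, which are the ones for which this bias matters. Two analysts could enter the score in different forms and report different drug effects, one of which might not answer the stated question.

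**Working it through.** **Plan's own figure.** Section 7.2 and Table 1 use a two-sided paired t test with dz 0.5, alpha 0.05 and n = 34. Noncentrality = 0.5 × √34 = 2.915; critical t on 33 df = 2.0345; power = 0.8078, which agrees with the table. Enrolment: 34 / 0.8 = 42.5, rounded up to 43, also as stated.

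**Case A: one value per subject.** Write craving in each Stage as subject effect + drug effect + β × score. The score is the same in both Stages, so it cancels from the within-subject difference:

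(drug + βx) − (placebo + βx) = drug − placebo.

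Among completers the drug contrast is then the paired mean difference, whether or not the covariate is retained. A numerical check on simulated two-Stage data gave the same coefficient with and without the covariate (−0.21197 both times). Expected estimate 0.50, power 0.81. This holds for a main effect, or for a centred score. It holds even if the single value averages on-treatment scores.

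**Case B: one value per Stage.** Assumptions, none from the documents: total effect 0.5 on craving; the drug lowers negative affect by δ; r is the correlation between within-person changes in affect and craving. Effects and δ are in SDs of within-person change. Regressing the craving difference on the affect difference gives

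adjusted drug coefficient = 0.5 − r × δ,

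with approximate standard error √[(1 − r²)(1 + δ²) / 34]. For r = 0.5 and δ = 0.5 the coefficient is 0.5 − 0.25 = 0.25, the standard error √(0.75 × 1.25 / 34) = 0.166, and the ratio about 1.5. Power by simulation (40,000 runs per setting):

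| δ | r = 0.3: coefficient, power | r = 0.5: coefficient, power |
|---|---|---|
| 0 | 0.50, 0.83 | 0.50, 0.89 |
| 0.1 | 0.47, 0.78 | 0.45, 0.82 |
| 0.25 | 0.425, 0.67 | 0.375, 0.65 |
| 0.5 | 0.35, 0.45 | 0.25, 0.30 |

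If affect worsened by 0.5 SD instead, the coefficient would rise to 0.65 or 0.75. With no total effect and a 0.5 SD shift, the test would reject in about 12% (r = 0.3) or 31% (r = 0.5) of trials instead of 5%.

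**Which case does the text describe?** The drug condition is the within-subject factor, and repeated measures ANCOVA is commonly run with one covariate value per subject. Negative affect shares its sentence with cannabis dependence, a subject-level characteristic. The next sentence adds further covariates and calls them baseline characteristics. This favours Case A without proving it. No passage describes a Stage-by-Stage covariate.

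**The case for a change.** The best argument for a change is that clarification is cheap and the point is not settled by the text. Sections 5.3 and 5.4 already plan a covariate that can arise after dosing: cannabis use detected on return from leave between Stages. So one cannot assume that every covariate here is pre-dose. Even if the Study Outline lists assessment days, it need not say which one feeds the model. For the AE co-primary, section 10.1 names headache and stomachache among the commonest earlier side effects, and a pain score taken on treatment could pick up the same complaints.

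The ambiguity stands, and so does the principle about on-treatment covariates. The rest carries less weight. The cannabis rule shows that one post-dose covariate is intended, not that mood scores are used by Stage. The AE argument needs the covariate to be a pain score, whereas section 7.1 enters negative affect; the checklist items are not given, and any size would rest on assumed event rates.

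The stronger remedies have their own difficulties. A general bar on covariates measured after first dosing would contradict the cannabis provisions. An added pre-dose administration cannot reach people already treated: section 10.1 carries a May 2022 update from this study's conduct, and this version is dated September 2023. A pre-dose main effect would also add nothing to the drug contrast, as Case A shows.

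**Conclusion.** No change follows. Section 7.1 leaves out a detail that an analyst would ordinarily supply by using one value per subject. The contrast is then unbiased and power stays at the planned 0.81; the sample sizes of 34 and 43 are unaffected.

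Harm needs three things together: Stage-specific scores in the model, a GLWL-01 effect on those scores, and a relation between score and outcome. The retention rule makes the third likely, but the documents support neither of the first two. The severe losses (power 0.30 to 0.45) also assume a mood shift as large as the planned craving effect, after a minimum of four days' dosing. At a shift of 0.1 SD power is 0.78 to 0.82, close to plan. If the drug does not move mood, Stage scores would raise power slightly, to between 0.83 and 0.89.

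This conclusion rests on the usual form of repeated measures ANCOVA, with the score centred or entered as a main effect, and on complete pairs. It would not cover a report that adjusted the primary contrast for on-treatment scores.

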7.3 Accrual number

Consistent with the within-subject design and other human laboratory studies we and others have performed, we anticipate that approximately 20% of the enrolled participants may not complete the study. Therefore, we anticipate enrolling up to 43 participants in order to reach up to 34 completers.

PI Name: [name]., Ph.D., M.Sc.

Abbreviated Title: GOAT

Version Date: 09/25/2023

8 HUMAN SUBJECTS' PROTECTION PLAN

8.1 ***Consent documents and process***

Procedures conducted before obtaining consent for this protocol

Screening: subjects are prescreened during a phone screening which is part of the NIDA screening protocol. Then, potential candidates are screened in-person under the NIDA screening protocol, which will provide the necessary data to determine eligibility to this protocol.

Clearance for eligibility: inclusion/exclusion criteria will be reviewed by a team of three individuals and signatures will be required in order to establish participants' eligibility to this protocol. Once cleared for eligibility participants, will be contacted and scheduled for consent procedures.

8.1.1 Consent procedure

On the day of consent eligible participants will undergo an alcohol and drug screening. A positive BAC or urine drug screen (benzodiazepines, barbiturates, cocaine metabolites, morphine, oxycodone, methadone, amphetamine, & buprenorphine and/or any other clinical condition requiring further assessment and evaluation may result in consenting procedures being either rescheduled or the participant being classified as ineligible. Eligible subjects are enrolled in this protocol after the study-specific consent form for this protocol is obtained. Authorized study investigators will obtain informed consents for this protocol. All participants will receive a verbal explanation in terms suited to their comprehension of the purposes, procedures and potential risks of the study and of their rights as research participants as detailed in the consent form. Participants will have the opportunity to carefully review the written consent form and ask questions regarding this study prior to signing as a copy of the consent will be handed to the participant during their screening visit and again on the day of consent. Participants will be asked to sign and date the informed consent. A copy of the signed and dated consent will be given to each participant. As part of the consent procedure, participants' ability to understand the consent will be evaluated using the 'NIDA/NIAAA Evaluation of Potential Research Participants' Ability to Consent'. Subjects must answer all questions correctly to proceed with consent signing.

Consent Review Process (in person or remote)

After the potential participant has had the opportunity to review the consent form, the PI or co-investigator may conduct the verbal review of the consent form a. in a face-to-face discussion in a private study room or b. via encrypted video chat program or c. via a remote-onsite video conference between on-site private study rooms, all approved by NIDA's ISSO. The remote platforms allow a virtual face-to-face interaction which we believe enhances the consent process while also reducing person-to-person contact. The format to be used will be decided by the PI or co-investigator in consultation with the prospective participant. Regardless of the platform selected for the review of the consent, e.g., face to face or remote from outside of NIDA or within NIDA's physical space, the PI/co-investigator will obtain the signature of the participant in person only after answering all questions and confirming participant

PI Name: [name]., Ph.D., M.Sc.

Abbreviated Title: GOAT

Version Date: 09/25/2023

understanding of the protocol including completion of the NIDA/NIAAA Evaluation of Potential Research Participants Ability to Consent.

Consent Signing Process (paper or electronic)

Signatures will be obtained on the consent in-person only, there will be no remote consent signing process for this study. Signatures will not be obtained until a. the PI/co-investigator has verified the identity of the participant including confirmation of the individual's name and birthdate b. the PI/co- investigator has confirmed all questions raised by the prospective participant have been adequately answered and c. the PI/co-investigator have completed the NIDA/NIAAA Evaluation of Potential Research Participants Ability to Consent. Documentation will be provided confirming all three assessments have been completed in CDW on the day of consent.

The PI or co-investigator along with the participant have two options for applying their signature and date to the consent (PDF) document prior to uploading in the electronic medical record in CDW. a. manual pen/paper signing may take place. Once the participant and PI/co-investigator have both manually signed and dated the paper consent, a member from the research team will scan and upload the signed consent into CDW or b. electronic signing may take place on the PDF consent document. Adobe Acrobat endorsed by the NIH and is the approved program installed by NIDA BIS to allow for the safe and secure electronic signing of PDF documents in CDW and is 21 CFR part 11 compliant. The following steps will be followed to obtain electronic signatures.

1. The PI/co-investigator log into CDW using their unique identification code/password. This ensures the authenticity, integrity and confidentiality of electronic records by authorized individuals.
2. Open the PDF document to be signed on the designated government approved device (laptop/tablet)
3. Click the Sign icon (alternatively click 'Fill & Sign') in the toolbar.
4. Hover the mouse over the field on the PDF where you want to add your signature and date
5. Use the stylus to import a signature image in the selected field.
6. By default, the signature color is black
7. Click apply and then click at the place in the PDF where you want to place the signature.
8. Click save, when you save the document, the signature, and date become part of the PDF and a permanent record in the participant electronic medical record in CDW.

Whether the consent is signed via pen/paper or electronic, the signed/dated copy of the consent will be printed out and delivered to the participant on the day of consent. Note, only CDW (EISnet) network compatible printers can be used to print out signed consent documents on site at NIDA further ensuring restricted access to documents containing PII to authorized personnel only and on an as needed basis.

8.2 Subject Selection

Adults who fulfill the qualification criteria will be included, regardless of race, ethnicity, sex, or religious

PI Name: [name]., Ph.D., M.Sc.

Abbreviated Title: GOAT

Version Date: 09/25/2023

affiliation. Individuals must be able to speak, read, write, and understand English as this study employs scales and experimental procedures that are validated only in English. This includes the assessments conducted to test the primary and secondary outcomes and is therefore required to maintain the research integrity of the study.

8.3 Recruitment

Consistent with the other clinical protocols in the NIDA IRP, recruitment efforts will take place as part of the NIDA screening protocol. Participants will be recruited through referrals from the NIDA Recruitment Contractor, NIH Volunteer Office, NIH clinicians and from the NIH Office of Patient Recruitment as well as through ResearchMatch.org (facilitated through OPR). ResearchMatch is a voluntary service that matches people interested in being research participants with researchers conducting a wide range of studies.

ResearchMatch is currently used for other protocols in our Section, as well as for many other NIH protocols. ResearchMatch is a Clinical and Translational Science Awards (CTSA) initiative funded by the National Center for Advancing Translational Sciences (NCATS), part of the National Institutes of Health. Furthermore, participants will also be recruited by word of mouth and through local pre-approved advertisements created by the recruitment contractor. Advertisement language will be used as flyers with tear off tabs, posted on the NIDA and Johns Hopkins campuses and universities, colleges, local business establishments and medical institutions in the greater Baltimore Maryland metro area and in the DC area. Additionally, advertisements will be placed on billboards of public places and public transportation services in the greater Baltimore metro area. Advertisements will also be posted on the radio, in electronic (including social media) and printed local media, including newsletters, websites, and local newspapers in the greater Baltimore area (for example, the 'Baltimore Examiner'). Listserv ad will be used on craigslist.org, as well as in NIH and other local email distribution lists, that are moderated, and following approval from the managers of these lists. 'ClinicalTrials.gov' may also represent a source of recruitment. Finally, participants will also be recruited via the NIDA Screening Protocol), as these protocols serve as the screening protocols not only for this study but also for other protocols at the NIDA Intramural Clinical Program.

8.4 Children

Children < 18 years of age will not be studied.

8.5 Vulnerable populations

Vulnerable populations will not be studied.

8.6 Evaluation of Risks/Discomforts and Benefits ratio

Anticipated Benefit

This study does not offer direct benefit to participants.

9 PROTECTION OF PARTICIPANTS' PRIVACY AND CONFIDENTIALITY

PI Name: [name]., Ph.D., M.Sc.

Abbreviated Title: GOAT

Version Date: 09/25/2023

This protocol will be covered by a Certificate of Confidentiality (CoC). Strict subject confidentiality will be maintained throughout the study. Confidentiality and information technology standards are in place at the NIDA intramural program to protect electronic repositories of patient data as well as other clinical patient related material. It is reasonably expected that these safeguards will protect participants' medical and personal health information, ensuring their privacy.

Information obtained in the course of participating in this protocol will become part of the patient's NIH medical record. Third parties may request access to this information. However, access will not be granted without the explicit, written consent of the subjects. Samples and data will be stored using codes (protocol number plus participant study number) that we assign. Only the PI, MAI, AIs and authorized staff can link the codes back to the subject's identity. Data will be kept in password protected computers. Samples will be kept in locked storage. Only study personnel will have access to the samples and data.

